8.2.2 Inclusion Criteria

The inclusion criteria for the RCT will mirror the FFF program's eligibility criteria:

- Type II Diabetes and an HbA1c ≥ 8.0 as determined in Geisinger EMR. The most recent HbA1c value within the past 12 months will be used to determine eligibility.
- 2. Food insecure based on a two-question survey instrument
- 3. Age \geq 18 and age \leq 85
- 4. Living within geographic reach of the program
 - a. Lewistown, PA
 - b. Scranton, PA

[figure not shown]
If the study is unable to reach its enrollment goal within 1 year, the HbA1c inclusion criteria for the study and program may be reduced to $\geq 7.5\%$.

Patients should meet the above clinical criteria and be of able mind and body to participate with the educational, consultative and food provisional services. In addition, patients should understand and speak English.

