8.4 Procedures

Baseline biometric measures (HbA1c, fasting glucose, weight, BMI, blood pressure and lipid panel) will be collected utilizing the most recent values available in the subjects' medical records within the year prior to enrolling in the FFF study. These biometric measures will be used to determine eligibility for the study and during data analysis.

A set of blood tests (HbA1c, fasting glucose and lipid panel) will be collected for research immediately prior to the subject beginning the FFF program (month 0 for treatment group or approximately month 6 for the control group). In addition, research participants will complete a baseline survey upon entry into the FFF program. This survey will be completed on site at the FFF program clinic.

A set of research biometric measurements (HbA1c, fasting glucose, weight, BMI, blood pressure and lipid panel) will be collected at approximately the 6 and 12 month time points (plus or minus

1 month) for the treatment group. A set of research biometric measurements (HbA1c, fasting glucose, weight, BMI, blood pressure and lipid panel will be collected at approximately the 12 month time point (plus or minus 1 month) for the control group.

In addition, all research participants will complete a survey after 6- and 12-months of participation (similar to the baseline survey) during FFF program visits. For those who do not enroll in the study, we will not continue to investigate their outcomes at these intervals.

Protocol required lab draws will be paid for by the study. Patients will be compensated with a \$50 gift card for the time and effort to complete the lab work and the patient surveys.

Based on our experience with the FFF program, we expect nearly all the patients to continue with the study. For the few who do drop out of the study but remain in the program, we will contact these subjects and collect outcome information, including clinical lab results and the ongoing survey. For those who drop out of the FFF program, but remain in the study the lab work will be covered by the research study and the surveys will be completed by phone or e-mail. The patients will be offered a \$50 gift card as compensation.

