9.1.1 Statistical Analysis Plan

For both specific aims, we will estimate intent-to-treat models using Ordinary Least Squares regression. Consider an outcome, Y_i , such as HbA1c, for each subject i. The estimating equation is:

$$Y_i = \beta_0 + \beta_1 1 (\text{Treatment})_i + \beta_2 X_i + \varepsilon_i$$

For the historical data analysis, $1(\text{Treatment})_i$ is an indicator variable equal to one if the subject participated in the FFF program, and zero otherwise. For the prospective trial analysis, $1(\text{Treatment})_i$ is an indicator equal to one if the subject was randomized to the treatment group and zero if the subject was randomized to the control group; X_i is a vector of control variables. These control variables should be uncorrelated with the treatment indicator, but they can aid in

[figure not shown]
the precision of the estimate. We propose standard demographic and prior-utilization controls: age (5-year age bins), sex (indicator that the patient is male), race/ethnicity (indicators for African American and Hispanic), as well as the most recent outcome recorded prior to enrollment (HbA1c at the baseline visit). We will also include controls for the timing of the tests, including the number of days from baseline to the test and the month-year of enrollment in the study.

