# 4. Empirical Model

Our initial analysis will estimate intent-to-treat models using linear regression. Consider an outcome,  $Y_i$ , such as HbA1c, for each subject i. The primary specification is:

$$Y_i = \beta_0 + \beta_1 1(\text{Treatment})_i + \beta_2 X_i + \varepsilon_i$$

For our analysis,  $1(\text{Treatment})_i$  is an indicator equal to one if the subject was randomized to the treatment group and zero if the subject was randomized to the control group;  $X_i$  is a vector of control variables. These control variables should be uncorrelated with the treatment indicator, but they can aid in the precision of the estimate because they are correlated with the outcome Y. First, we will include strata indicators for location and HbA1c category. We will also include the lag of the dependent variable, which substantially improves power: for clinical test results that would be the most recent test result prior to enrollment in the study. For utilization outcomes such as inpatient visits, we will include the number of such episodes observed in the 12 months prior to study enrollment.

We also plan to include standard demographic controls: age (5-year age bins), sex (indicator that the patient is male), race/ethnicity (indicators for African American and Hispanic). For the clinical test results, we will also include a control for the number of days from the baseline measure to the follow-up test in order to improve precision. If this number of days is not balanced across treatment and control, we will control for the number of days between the baseline test and the date of enrollment into the study. We will also include the month-year of entry into the study unless this measure is highly correlated with the number of days between blood tests and reduces statistical precision.

We will also estimate models where the outcome is the difference between the baseline and the follow-up exam instead of including the baseline exam result as a control:

$$\Delta Y_i = \beta_0 + \beta_1 1 (\text{Treatment})_i + \beta_2 X_i + \varepsilon_i$$

This is a more restrictive model but may improve statistical precision and requires fewer controls. For models that control for lagged values or in this difference model, we will estimate models for those with non-missing values. We will also test whether missing lagged value is balanced across treatment and control for each measure. Note that all patients have a baseline HbA1c that was used in recruitment.

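### The primary HbA1c model adjusts for an interval that ends after randomisation, and its covariate set is not fixed before outcome data are seen

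*SAP*

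**What the plan says.** SAP section 4 builds the primary specification from strata indicators, the lagged outcome, demographics and timing terms. It says of the controls: "These control variables should be uncorrelated with the treatment indicator". The lag is defined thus: "for clinical test results that would be the most recent test result prior to enrollment in the study". Protocol 8.2.2 lets that result be up to a year old: "The most recent HbA1c value within the past 12 months will be used to determine eligibility".

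For clinical results the SAP then adds: "we will also include a control for the number of days from the baseline measure to the follow-up test". It follows with a switch: "If this number of days is not balanced across treatment and control, we will control for the number of days between the baseline test" and enrolment instead. It does not say how balance is judged. Month-year of entry is also included, "unless this measure is highly correlated with the number of days between blood tests and reduces statistical precision".

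Protocol 9.1.1 lists the timing controls without conditions, "including the number of days from baseline to the test and the month-year of enrollment in the study". It has neither the switch nor the exception for month-year.

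The month-6 test is triggered differently in each arm. Protocol 8.4 places the treatment-arm measurement at about 6 months, plus or minus 1 month. The control-arm draw comes just before programme start, at roughly month 6, with no stated window. SAP section 2 has staff contact controls at month 5 to book that start.

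**The concern.** Days from baseline test to follow-up test (D) is the sum of two parts. A, from baseline test to enrolment, is fixed before randomisation. B, from enrolment to follow-up test, is not. Randomisation makes A independent of arm but gives no such guarantee for B, so D need not meet the SAP's own condition on its controls. If mean B differs by arm, adjusting for D moves the treatment estimate by the fitted slope times that difference.

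The switch shows that the SAP saw this risk. However, it rests on an undefined check of the total, and the wide spread of A can hide a shift in B. Judging whether month-year reduces precision means fitting the outcome model first. The plan was written as a record against searching for results afterwards, and the academic researchers monitor interim results throughout. An open choice of primary covariates therefore weakens the plan even if the numerical effect is small.

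**Working it through.** **Inputs from the documents.** N = 500, 1:1, alpha 0.05, power 80%. HbA1c at 180 days: mean 8.58, SD 1.74, sqrt(1-R²) 0.66, target 10%, required N 55 (Table 2). Stated intent-to-treat detectable effect 3.7%. Baseline result up to 12 months old. Treatment-arm window plus or minus 1 month.

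**Assumptions, not in the documents.** A is uniform over 0-365, 0-180 or 0-90 days. B is uniform over plus or minus 30 days in both arms (SD 60/√12 = 17.3). Balance is judged by a two-sided 5% test of means. There is no attrition.

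**1. The plan's own figure.** Residual SD = 1.74 × 0.66 = 1.148 and the target is 0.858. N = 4 × (1.960 + 0.842)² × 1.148² / 0.858² = 56.2, against 55 stated, which is close enough to use 1.148. The yardstick is 3.7% × 8.58 = 0.317 points. A closed form at N = 500 gives 2 × 2.802 × 1.148 / √500 = 0.288 (3.35%). The simulated 3.7% is thus not reproduced, and the SAP does not state its simulation inputs.

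**2. Power of a balance check on D.** SE = 2 × SD(D) / √500 and power = Φ(Δ/SE − 1.96), where Δ is the arm difference in mean days.

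| Span of A (days) | SD(D) | Share of Var(D) from A | SE | Δ = 7 | Δ = 15 | Δ = 30 |
|---|---|---|---|---|---|---|
| 0-365 | 106.8 | 97% | 9.55 | 11% | 35% | 88% |
| 0-180 | 54.8 | 90% | 4.90 | 30% | 87% | about 100% |
| 0-90 | 31.2 | 69% | 2.79 | 71% | about 100% | 100% |

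For example, Φ(15/9.55 − 1.96) = Φ(−0.39) = 0.35. A check on B alone (SE 2 × 17.3/√500 = 1.55) would detect 2.80 × 1.55 = 4.3 days with 80% power. On D with the widest span the figure is 26.8 days.

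**3. Size of the bias.** In a linear model with a common slope, and if the timing gap does not itself move HbA1c, the error is γΔ. Here γ = [ρ × 17.3 × 1.148 + g × Var(A)] / Var(D). The correlation ρ between B and the HbA1c residual is assumed to be 0.3-0.5, and the slope g on A 0-0.002 points/day. Under the SAP rule the expected error is about (1 − power) × γΔ.

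- The largest value over the three spans and shifts of 1-60 days is at span 0-90, ρ = 0.5, g = 0.002. γ = (9.93 + 1.35)/975 = 0.0116. At Δ = 5, power is 43%, so the error is 0.57 × 0.0116 × 5 = 0.033 points, or 10% of 0.317.
- The maxima for the other spans are 0.026 (0-180) and 0.028 (0-365). With the mildest assumptions (ρ = 0.3, g = 0, span 0-365) the maximum is 0.005.
- If every baseline test had the same age, the maximum would be 0.051 (16%).
- Without the switch, as in the protocol, a 15-day shift gives 0.008-0.042 (0-365), 0.030-0.077 (0-180) or 0.09-0.17 (0-90).

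Simulation (N = 500, 3,000 runs per scenario) flagged a 15-day shift 35-37% of the time for the widest span. Adjusting for A alone gave a bias within ±0.004 in every scenario.

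**4. Direction.** Suppose HbA1c depends on A at 0.5-1.0 points/year and not on B. With span 0-365 and a 15-day gap, always adjusting for D is off by 0.974 × (0.5 to 1.0) × 15/365 = 0.02 to 0.04, and adjusting for A is off by about 0. Suppose instead that HbA1c drifts with total elapsed time at the same slopes. Then adjusting for D is off by about 0. Adjusting for A differs from a same-day comparison by (0.5 to 1.0) × 15/365 = 0.02 to 0.04.

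**The case against.** A reader might infer that the balance check is too weak to do its job and that the HbA1c estimate is therefore biased. The documents do not support that. They set a 12-month limit on baseline age but give no distribution, and the power of the check runs from 35% to about 100% for the same shift. Bias in a linear model scales with the mean difference in days, so a check on means looks at the right quantity. Where the check is weak, the spread of A also dilutes the slope. Where the slope could do harm, the check has high power.

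Nor do the documents show a timing gap. Both arms aim at month 6, and outreach to controls at month 5 serves that aim. The SAP's fallback is already a sound pre-randomisation covariate. Two of its three reported specifications, strata only and strata plus lag, omit the days term, so a distortion should be visible.

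The rule for month-year is also narrower than it may look. Both conditions must hold, the first needs no outcome data, and the second uses the standard error rather than the effect estimate.

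All of this stands, and it limits the size of the problem. It does not supply a criterion for balance, settle which model is primary, or give the protocol a fallback.

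**Conclusion.** The point holds as one of specification. The primary model conditions on a partly post-randomisation interval. The safeguard has no criterion and can miss an arm difference of one to two weeks if baseline tests are spread over most of the permitted year. The two documents give different rules, and the final covariate set depends partly on outcome-model precision.

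The consequence under the SAP's rule is small: up to about 0.03 points, about 10% of the stated detectable effect, for the three baseline-age spans tried. That rests on the assumed spans, window, correlations, slopes and 5% test. The sign cannot be given, because it depends on whether HbA1c follows baseline age or total elapsed time. The protocol's unconditional version is the more exposed. The case for change is that the choice can be settled in advance at almost no cost, not that the trial's result is in danger.

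**What to change.** - In SAP section 4 and Protocol 9.1.1, name days from baseline test to enrolment as the timing covariate in the primary model for clinical results, unconditionally. Delete the balance-triggered switch.
- State that calendar time of entry (month-year, or quarter) is in the primary model whatever it does to the standard error.
- Report enrolment-to-test days by arm. Keep the model with days to the follow-up test as a sensitivity analysis beside the strata-only and strata-plus-lag models already planned. This covers the case in step 4 where HbA1c drifts with total elapsed time.

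The cost is about two sentences in the SAP and one in the protocol, with no new data. If B has no effect of its own on HbA1c, adjusting for A gave a simulated standard error of 0.103, against 0.103-0.114 for D. Month indicators over the two-year recruitment cap would add about 23 terms. If they explained nothing, they would widen the standard error by about √(500/477) = 1.024, or 2.4%; quarters would cost less.

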## 3.3. Secondary outcomes

### *6-month outcomes*

Secondary outcomes of interest include other biomarkers at 6 months: fasting glucose, weight, BMI, blood pressure, total cholesterol, LDL cholesterol, and triglycerides.

We will also examine outcomes based on self-reported survey data, including diet, exercise, and other healthy behaviors, self-efficacy, self-assessed physical and mental health, and patient satisfaction with Geisinger Health as a whole. We will also measure whether the patients have improved their understanding of diabetes and healthy eating.

Other outcomes help us understand the nature of the services offered. The control group has access to dietitian consultations and diabetes self-management classes as part of the standard of care, but we believe the take-up of such services will be higher among the treatment group. We ask about these consultations and classes in the patient surveys to verify that this is the case. We also survey participants about adherence to diabetes best preventive care and whether the subjects are signed up for SNAP benefits, as the program encourages take-up.

Using encounter data, we will also document the level of engagement with the program at the FFF clinic, including the number of weeks that the participants picked up food, the number of dietitian encounters, and the number of classes taken.

Health care utilization is another important secondary outcome. We will examine, at six months, the difference between the treatment and control group in: probability of any inpatient stay, any ED visit, any hospital visit (inpatient or ED). We will also examine the number of such visits, as well as the number of outpatient visits outside the FFF program. We will also examine medication usage, including insulin. Related, we will test for differences in paid claims both in those categories and in the amount paid among the Geisinger Health Plan beneficiaries and check that treatment and control are balanced on inclusion in this sample. We expect there may be outliers in payments, so we will estimate models in levels, logs, and check for differences in the distribution including the median. Any effect of the program on such outcomes may take time to materialize and thus may not be visible at 6 months.

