To consider robustness, we will report models with only strata indicators as controls, strata indicators plus the lag of the dependent variable because this substantially improves statistical power, and models with full controls.

The coefficient  $\beta_1$  measures the effect of intention-to-treat: the causal effect of being randomized into the treatment group. This can differ from the effect of the program if there is non-compliance: some subjects randomized to the treatment group may decide not to join the FFF program or may quit it after a short time. (Given the value of the free food, we expect that refusal and dropout rates will be low.) At the initial pilot site of Shamokin PA, 17% of those who began the program were no longer in the program at 6 months.

As an alternative specification, we will estimate the equation using Two Stage Least Squares (2SLS), with the initial randomized assignment to treatment or control used as an instrumental variable for the fraction of months engaged in FFF. The 2SLS estimate measures the average causal effect of the program for those who choose to remain in it as a complementary parameter to the intent-to-treat analysis described above.

That is, for subject i the structural equation is:

HbA1c at 6 monthsi = 
$$\beta_0 + \beta_1 \left\{ \left( \frac{1}{6} \right) * \text{Months of Engagement} \right\}_i + \beta_2 X_i + \varepsilon_i$$

And the first-stage is:

Months of Engagementi = 
$$\alpha_0 + \alpha_1 Treatment_i + \alpha_2 X_i + \vartheta_i$$

We re-scale the months of engagement in the structural equation by 6 for 6-month outcomes, and by 12 for 12 month outcomes so that the interpretation of our estimate of  $\beta_1$  is for full engagement, which eases comparisons to the intent-to-treat estimates.

In addition, if there is differential attrition from the study across treatment and control groups (despite our efforts to obtain outcomes from each subject including obtaining multiple forms of contact information for subjects and their family members and compensation for subjects' time)

we will explore bounding estimates under a range of assumptions about effect sizes for those not observed.

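### Lag-adjusted models for the secondary biomarkers drop subjects with no prior value, giving up precision that an efficient missing-baseline method would keep

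*SAP*

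**What the plan says.** SAP section 4 (Empirical Model) adds the prior value of the outcome to the primary specification: "We will also include the lag of the dependent variable, which substantially improves power". For clinical tests this is the latest result before enrolment. Two sentences deal with subjects who have no such value: "For models that control for lagged values or in this difference model, we will estimate models for those with non-missing values", and "We will also test whether missing lagged value is balanced across treatment and control for each measure". Neither document names an imputation, likelihood or missing-indicator method for them.

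HbA1c is exempt: "Note that all patients have a baseline HbA1c that was used in recruitment". No such assurance is given for the rest: "Secondary outcomes of interest include other biomarkers at 6 months: fasting glucose, weight, BMI, blood pressure, total cholesterol, LDL cholesterol, and triglycerides" (SAP section 3.3, with the same outcomes repeated at 12 months). Protocol 8.4 takes baseline values from the latest entries in "medical records within the year prior to enrolling in the FFF study".

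The research blood draw before programme start (Protocol 8.4) cannot fill a gap in both arms. It falls at month 0 in the treatment group but at about month 6 in controls, and it covers only HbA1c, glucose and lipids.

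Two other parts of SAP section 4 matter. For clinical tests the controls include the days from the baseline measure to the follow-up test, with days from baseline test to enrolment as a fallback. The SAP also commits to a range of models: "To consider robustness, we will report models with only strata indicators as controls", then strata plus lag, then full controls.

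**The concern.** A subject can be randomised, give a follow-up sample at the study's expense, and still be left out of the lag-adjusted and difference models because a test was not in the record before assignment. Each biomarker is then estimated in its own subset.

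The lag is included to gain precision, and dropping subjects gives part of that back. The three reported specifications also cease to be like for like. The strata-only model uses everyone with an outcome and the other two use fewer, so a change in the estimate between them mixes covariate adjustment with a change of sample.

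**Working it through.** **Inputs.** From the SAP power section: planned N 500, alpha 0.05, power 80%. The weight row (after 180 days) has mean 228, SD 64, sqrt(1-R2) 0.96, target effect 10% and required N 228. Allocation is 1:1 (Protocol 8.1). Assumed, because the documents do not give them: the share m with no prior value, and the lag R2 for the other biomarkers.

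**Reproducing the plan's figure.** Required N = 4 x [(1.960 + 0.842) x 64 x 0.96 / 22.8]^2 = 228, which matches. A one-sided test would give 180, so the table is two-sided.

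**Formulas.** Variances of the arm effect are in units of 4 x SD^2 / N, with the same outcome variance and the same treatment effect in subjects with and without a lag:
- Complete cases: (1-R2)/(1-m).
- Efficient use of everyone (inverse-variance weighting of the with-lag and without-lag groups): 1/[(1-m)/(1-R2) + m].
- Ordinary least squares with a missing indicator: 1 - (1-m) x R2.

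The complete-case to efficient SE ratio simplifies to sqrt[1 + m(1-R2)/(1-m)]. It is never below 1, and it approaches 1 as m falls to zero or R2 rises to one.

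| m | R2 | Complete-case variance | Efficient variance | Indicator variance | SE ratio, complete-case / efficient | SE ratio, complete-case / indicator |
|---|---|---|---|---|---|---|
| 5% | 0.44 | 0.589 | 0.573 | 0.582 | 1.015 | 1.006 |
| 5% | 0.20 | 0.842 | 0.808 | 0.810 | 1.021 | 1.020 |
| 20% | 0.44 | 0.700 | 0.614 | 0.648 | 1.068 | 1.039 |
| 20% | 0.20 | 1.000 | 0.833 | 0.840 | 1.095 | 1.091 |
| 30% | 0.44 | 0.800 | 0.645 | 0.692 | 1.114 | 1.075 |
| 30% | 0.20 | 1.143 | 0.851 | 0.860 | 1.159 | 1.153 |
| 20% | 0.80 | 0.250 | 0.238 | 0.360 | 1.025 | 0.833 |

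At 20-30% missing and R2 0.20-0.44, the complete-case SE is therefore 7-16% larger than the efficient one. The last row shows the limit of the simple method: at R2 0.80 the indicator SE is sqrt(0.360/0.250) = 1.20 times the complete-case SE. Setting the two variances equal gives a break-even R2 of 1/(2-m), which is 0.53, 0.56 and 0.59 at 10%, 20% and 30% missing.

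**The weight row.** Here R2 = 1 - 0.96^2 = 0.078 and N = 500. With nothing missing the detectable effect is 6.75% of the mean; unadjusted on all 500 it is 7.03%.

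| m | Complete-case detectable effect | Efficient | SE ratio | Complete-case power for a 10% effect |
|---|---|---|---|---|
| 10% | 7.12% | 6.78% | 1.05 | 97.6% |
| 20% | 7.55% | 6.81% | 1.11 | 96.0% |
| 30% | 8.07% | 6.83% | 1.18 | 93.5% |

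Complete-case adjustment is less precise than no adjustment on everyone once m exceeds R2, here about 8%. Power for the 10% target stays at 80% or more until 228 of 500 remain, that is, until about 54% are missing. The documents do not say whether 0.96 includes lagged weight, so this row is only an illustration.

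**Simulation check.** In 4,000 simulated trials of 500 subjects at 20% missing, the empirical SEs (complete-case against weighted) were 0.098 against 0.088 at sqrt(1-R2) 0.96, and 0.0661 against 0.0630 at 0.66. This agrees with the formulas.

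**The case against.** The plan's rule is pre-specified and defensible for secondary outcomes. The SAP tests whether missing lags are balanced by arm, and it reports a strata-only model that keeps every subject with an outcome. Missingness may be low: all subjects are Geisinger patients with an HbA1c in the past 12 months, and the SAP's definition of the lag, unlike Protocol 8.4, sets no one-year limit. At 5% missing the gain is only 1-2%. All of this stands, and it limits the size of the point. None of it supplies a lag-adjusted estimate on all subjects with an outcome.

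The obvious remedy is also open to challenge. A missing indicator can be less precise than complete cases, and filling only the lag would still lose the subject from the full-control model, because days from baseline is missing too. Both objections are right, and they determine the choice of method below.

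A reader might infer three stronger things that the documents do not support:
- That the primary result is affected. It is not, because baseline HbA1c is complete.
- That the rule biases the treatment effect. Whether a prior value exists is settled before assignment, so arms within the subset remain comparable; the estimate simply describes that subset.
- That the secondary biomarkers become underpowered. The weight row does not show this at any plausible rate.

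**Conclusion.** The point holds as a minor refinement. For biomarkers other than HbA1c, the lag-adjusted models lose randomised subjects who have a 6- or 12-month result, and with them some precision. At an assumed 20-30% missing and lag R2 of 0.20-0.44, the complete-case SE is about 7-16% larger than it need be. With few missing values or a strongly predictive lag, the difference is close to nothing. The actual rates and lag R2 values are not in the documents, so the loss in this trial cannot be fixed more closely. The figures also assume that outcome variance and treatment effect are alike in subjects with and without a prior value.

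**What to change.** In SAP section 4, for the lag-adjusted models of secondary biomarkers:
- Keep all randomised subjects with an outcome by multiple imputation of the missing lag, by a likelihood method, or by precision-weighting the with-lag and without-lag estimates. Use baseline HbA1c as a predictor. An imputation model should also contain arm and the follow-up outcome, with enough imputations that simulation error is negligible. Done this way, the method should not be less precise than complete cases at any R2.
- Allow a simple missing indicator only where the lag explains less than about half the variance.
- Handle the timing covariate the same way, for example by using days from enrolment to the follow-up test, subject to the SAP's existing check on balance between arms. The SAP's fallback (days from baseline test to enrolment) is missing with the lag and would need imputing as well.
- Keep the complete-case results as a sensitivity analysis and for the change-score model. Report the number of subjects in each specification.

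The SAP's introduction already provides for dated additions. Because the analysts monitor interim results, the method should be fixed before it could be influenced by them. The cost is a few sentences, slightly more analysis work, and some modelling assumptions for secondary outcomes.
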